The Health Advocate builds a supportive, coaching relationship with the patient and provides non-clinical support, encouragement, and accountability to maximize engagement. The Health Advocate sends encouraging messages and addresses patients’ non-clinical needs, facilitates patient adherence to care programs, promotes patient program retention and engagement through multiple communication channels, and monitors the patients’ Mobile App behaviors. As a part of these activities, the Health

Advocate directly encourages patients to complete the tasks in their Wellframe care program, including reading their health education and completing their surveys.

The Health Advocate co-manages patients with the clinical team via the Wellframe dashboard. The Health Advocate facilitates triage of clinical needs to clinical staff. As a non-clinician, the Health Advocate operates under the supervision of Wellframe's team of licensed clinicians (physicians and nurse practitioners), and all patient communication adheres to structured protocols and guidelines set forth by Wellframe clinical leadership.

III. RESEARCH DESIGN AND METHODS

Sample size: 150 post-PCI at Massachusetts General Hospital (MGH) and Brigham & Women's Hospital (BWH): 100 with myocardial infarction, 50 with symptomatic coronary artery disease without myocardial infarction

Inclusion/Exclusion Criteria

- Acute myocardial infarction – defined by typical symptoms, characteristic kinetics of cardiac biomarkers or characteristic EKG changes

Or

Symptomatic coronary artery disease without myocardial infarction – defined by typical symptoms (i.e. angina) and signs (i.e. abnormal non-invasive cardiovascular testing: stress testing or coronary CTA)

Inclusion Criteria

- Age 21-85
- English-speaking
- PCI: balloon angioplasty, bare-metal stent, or drug-eluting stent at MGH
- Smartphone or Tablet (iOS or Android)
- Long term provider in Massachusetts (or records available through Care Everywhere)

Exclusion Criteria

- Recent (within 1mo) illicit substance use or alcohol abuse
- In-hospital AMI
- Known pregnancy
- Dementia or cognitive disability
- Incarceration

Study Outcomes

Clinical and Utilization Outcomes

Clinical outcomes will be ascertained from electronic medical records. Patients will also be called at 90 days to determine potential readmission, representation, and cardiac rehabilitation enrollment at other hospitals or clinics during the follow-up period. The following outcomes will be assessed:

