Throughout the study, Subjects will also be asked to complete surveys on Wellframe to assess process outcomes. The survey questions are listed in the attachment titled “Data”.

Study Closeout and Post Study Follow-up

Lastly, after 90 days, subjects who are enrolled in the study will be contacted by a member of the study staff to determine clinical outcomes: potential readmission, representation, and cardiac rehabilitation enrollment at other hospitals or clinics during the follow-up period. We will review the health records of both eligible but discharged and study subjects at 90 days to determine these same clinical outcomes at MGH. Subjects will be reminded during the 90 day phone call that they should delete the Wellframe application.

IV. RISKS TO SUBJECTS

Since the study involves adding a mobile health component to a treatment plan, risks posed to subjects are similar to those involved with following a post-PCI care plan. Subjects will be encouraged to contact their physician with medical questions.

Loss of privacy is a risk of this study that will be minimized by keeping patient health information in a secure database. Only study personnel who have undergone the proper human research training and signed standard confidentiality agreements will have access to this data.

Wellframe also has access to the data on patients' applications. The Wellframe platform, comprised of web-based and mobile solutions, is architected to protect the security of patient information. All data for the platform is stored on cloud servers and only pulled into the platform when accessed by clinician (web-based dashboard) or patient (mobile app). The Wellframe system encrypts patient data at rest and in transmission, and adheres to network security, server security and access control parameters in accordance with HIPAA privacy and security rules.

Clinician Dashboard: By encrypting data in-transit between the browser and services, Wellframe ensures that only authenticated users have access, requires complex passwords, and enforces automatic timeout user sessions.

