A Smartphone-based Application Post-myocardial Infarction to Manage Cardiovascular Disease Risk
NCT03416920
Version Date: 12/28/19
[name], [name]
Statistical Analysis Plan

A. Background and Rationale:

The period between inpatient hospitalization for symptomatic coronary artery disease (CAD) and post-discharge office consultation remains a vulnerable interval for adverse outcomes. We sought to develop and evaluate a tool to help guide, reassure and educate patients during this susceptible time.

We aimed to recruit and onboard 150 patients who have undergone percutaneous coronary intervention (PCI) with a novel mobile health platform developed specifically for this population. The mobile application (app) includes educational about specific procedures (PCI) and diagnoses (coronary artery disease, acute myocardial infarction) as well as lifestyle education programs (hypertension, hyperlipidemia, diabetes, weight loss, smoking cessation). The app also utilizes live health care coaches to interact with participants virtually to facilitate adherence to outpatient follow up, enrollment in cardiac rehabilitation and achieve individually targeted goals.

B. Hypothesis:

Our overall hypothesis is that engagement with our smartphone application post PCI will correlate with increased rates of enrollment in cardiac rehabilitation amongst study participants as compared to historical controls.

C. Endpoints:

- C.1. Primary:** 90-day cardiac rehabilitation enrollment rates
- C.2. Secondary:** 30-day cardiac outpatient follow up attendance

D. General Study Design and Plan

- D.1. Design:** Multi-site stratified single-arm prospective study

- D.2. Type of controls:** Historical

D.2.a. Control ascertainment: Query of Research Patient Data Registry (RPDR) database (a centralized clinical data registry that gathers clinical information from various Partners hospital systems with a query tool that provides users with detailed medical record information on identified patient populations that meet user-defined characteristics and criteria such as diagnoses, procedures, medications and/or laboratory results) for subjects aged 21-85 years old who underwent percutaneous coronary intervention from 01/01/2015 through 12/31/2017.

D.2.b. Control matching: Controls matched for Age, Sex (M/F), State (MA/non-MA), PCI Type (MI/Elective), DM2 (Y/N), Partners PCP (Y/N), Insurance Type (Commercial/Medicaid/Medicare/Other), Site (MGH/BWH)

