- D.3. Level and method of blinding:** Open-label

- D.4. Randomization time point:** NA

- D.5. Timeframe of all study periods:**

D.5.a. Intervention arm: screening (02/2018-06/2019), baseline (02/2018-06/2019), intervention period (02/2018-09/2019), follow-up (05/2019-09/2019)

D.5.b. Historical control arm: baseline (01/2015-12/2017), follow-up (03/2015-03/2018)

D.6. Inclusion/Exclusion criteria:

D.6.a: Inclusion: 21-85 years old, fluency in English language, underwent PCI at either MGH or BWH during screening period for either symptomatic CAD or ACS, own a smartphone or tablet

D.6.b: Exclusion: Recent (<1mo) drug or alcohol abuse, in hospital AMI, pregnancy, cognitive delay/dementia, incarceration

D.7. Study variables:

Age	Age at time of enrollment into study as coded into Partners EHR
Sex	Gender as coded into Partners EHR
State	State of residence (Massachusetts vs Non-Massachusetts) at time of enrollment into study as coded into Partners EHR
PCI Type	Reason for percutaneous coronary intervention (PCI). Myocardial infarction (MI) coded as chart diagnosis of MI or positive serologic (troponin) values prior to PCI. All other PCI without evidence of myocardial necrosis coded as elective.
Partners PCP	Coded "yes" for patients with PCP in Partners EMR working primarily for Partners Healthcare system. Coded "no" for patients with PCP in Partners EMR not within Partners system or missing PCP data.
Insurance Type	Coded based on primary insurance listed in Partners EMR.
Site	Coded based on location of incident PCI procedure (either Massachusetts General Hospital [MGH] or Brigham and Womens Hospital [BWH])
Hypertension	Chart diagnosis of HTN prior to or at time of incident PCI
Hyperlipidemia	Chart diagnosis of HLD prior to or at time of incident PCI, LDL-C >129 at time of incident PCI or Triglycerides >150 at time of incident PCI
Type 2 Diabetes	Chart diagnosis of DM2 prior to or at time of incident PCI, or Hemoglobin A1c > 6.4 at time of incident PCI
Peripheral Arterial Disease	Chart diagnosis of PAD prior to or at time of incident PCI or history of peripheral arterial intervention
Smoking	Chart history of smoking (codified as current smoker, former smoker (quit >1 month prior to PCI), or never smoker). For analysis, variable was condensed into never smoker or ever smoker (either current or former).
Coronary Artery Disease	Chart diagnosis of CAD prior to or at time of incident PCI or history of CABG or prior PCI

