30-day hospitalization	Admission date to a Partners hospital within 30 calendar days of incident PCI.
90-day hospitalization	Admission date to a Partners hospital within 90 calendar days of incident PCI.
Cardiac reason for hospitalization	Admission for chief complaint of cardiac etiology (ie CAD, CHF, arrhythmia), admission requiring cardiac consultation or admission to a cardiology ward unit.
30-day ER visit	Presentation to Partners ER or Urgent Care within 30 calendar days of incident PCI without subsequent hospitalization.
90-day ER visit	Presentation to Partners ER or Urgent Care within 90 calendar days of incident PCI without subsequent hospitalization.

90-day Cardiac Rehabilitation	Attendance of cardiac rehabilitation intake session at a Partners facility within 90 calendar days of incident PCI.
30-day Cardiac Follow Up	Attendance of cardiac outpatient follow up appointment at a Partners facility (with MD or NP) within 30 calendar days of incident PCI
30-day repeat PCI	Repeat percutaneous intervention on same or new coronary lesion within 30 days of incident PCI.
90-day repeat PCI	Repeat percutaneous intervention on same or new coronary lesion within 90 days of incident PCI.
90-day Stroke	Chart diagnosis of or admission for new stroke within 90 calendar days of incident PCI as noted in Partners EHR.
90-day Nonfatal MI	Chart diagnosis of or admission for myocardial infarction (without subsequent death) within 90 calendar days of incident PCI as noted in Partners EHR.
90-day CV Death	Documentation of death within 90 calendar days of incident PCI noted in Partners EHR with cause specified as secondary to CAD, CHF, Arrhythmia or other clear cardiovascular reason.
90-day All Cause Death	Documentation of death within 90 calendar days of incident PCI noted in Partners EHR.
Conversion Rate	Number of patients enrolled in Wellframe out of number of total patients eligible for study.
Days Enrolled	Number of days between patient onboarded with Wellframe app and marked done by clinical staff.
Medication Reminders	Number of medication reminders set up by patient (0 if patient has not set up any reminders).
30-day Medication Adherence	Percentage of medication reminder tasks completed within 30 days on app. (Null if no patient reminders set up)
90-day Medication Adherence	Percentage of medication reminder tasks completed within 90 days on app. (Null if no patient reminders set up)

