D.8. Sample size and power: We have at least 95 percent power with 150 enrolled participants, 450 matched historical controls, with alpha equal to 0.05, to detect an effect of at least 2-fold increase in the primary clinical outcome, likelihood of enrollment in cardiac rehabilitation within the 90 day study period with baseline 25% enrollment rates⁶.

E. General Considerations:

E.1. Analysis populations:

E.1.a.: Full analysis population: All intervention subjects who downloaded the study application and 3:1 matched historical controls.

E.1.b.: Engagement population: All intervention subjects who downloaded the study application.

E.2. Covariates and subgroups: Sex (M/F), State (MA/non-MA), PCI Type (MI/Elective), DM2 (Y/N), Partners PCP (Y/N), Insurance Type (Commercial/Medicaid/Medicare/Other)

E.3. Missing data: Missing data values for participants who fit inclusion criteria will default to zero or “no” for dichotomous variables. Missing data values for participants will default to “unknown” or “other” for continuous or categorical variables.

F. Summary of study data: All continuous variables will be summarized using the following descriptive statistics: n (non-missing sample size), mean, standard deviation, median, maximum and minimum. The frequency and percentages (based on the non-missing sample size) of observed levels will be reported for all categorical measures. In general, all data will be listed, sorted by site, treatment and subject, and when appropriate by visit number within subject. All summary tables will be structured with a column for each treatment in the order (Control, Experimental) and will be annotated with the total population size relevant to that table/treatment, including any missing observations.

G. Protocol deviations: Subjects who do not fit inclusion criteria will be removed from the data set prior to analysis. Subjects with missing data will be treated as discussed above (Section E.3.)

H. Efficacy Analyses: The Cox Proportional Hazards model will be used to assess efficacy of the intervention (use of the application) on the primary outcome. The percentage of subjects attending cardiac rehabilitation enrollment within 90 days of discharge from incident PCI hospitalization will be compared across groups. A secondary analysis between the two groups will be conducted adjusting for covariates such as age, sex, insurance type, state, diabetes, and partners PCP).

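### Controls are not screened for the provider-or-records criterion that app patients must meet, and Partners PCP cannot stand in for it in matching because it codes a missing PCP with a non-Partners PCP

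*SAP*

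**What the plan says.** **Eligibility of app patients.** The Inclusion Criteria in Protocol section III require a "Long term provider in Massachusetts (or records available through Care Everywhere"). The inclusion list in SAP D.6.a covers age, English and "underwent PCI at either MGH or BWH during screening period for either symptomatic CAD or ACS, own a smartphone or tablet". It has no provider or records criterion.

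**Eligibility of controls.** SAP D.2.a queries RPDR "for subjects aged 21-85 years old who underwent percutaneous coronary intervention from 01/01/2015 through 12/31/2017". Protocol section VII, which also draws controls from RPDR, adds no provider criterion either.

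**Matching factor.** SAP D.2.b ends its list of factors with "Partners PCP (Y/N), Insurance Type (Commercial/Medicaid/Medicare/Other), Site (MGH/BWH"). In D.7, Partners PCP has two levels, and *no* is used "for patients with PCP in Partners EMR not within Partners system or missing PCP data". The rule is not limited to one group.

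**Outcomes.** D.7 defines the primary outcome as "Attendance of cardiac rehabilitation intake session at a Partners facility within 90 calendar days of incident PCI". The 30-day follow-up outcome is likewise limited to Partners facilities.

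**The concern.** The two groups pass through different gates before they are matched. App patients had to show an established provider or accessible records; controls had only to be of the right age and have had a PCI in the right years. Matching could repair part of this if a factor carried the same information. Partners PCP is the closest, but its *no* level pools patients known to have a PCP outside Partners with patients whose PCP field is blank. Within that level, an app patient who met the criterion can be paired with a control for whom no PCP is recorded. The adjusted models in SAP section H and the table shells use the same two-level variable, so they cannot see the difference either.

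At stake is the control rate. Someone who came to MGH or BWH for a single procedure and has no recorded PCP may be less likely to return to a Partners rehabilitation programme or cardiology clinic. If such people are commoner among controls, the control rate falls for reasons unrelated to the app. SAP section K rests type I error control on this one primary outcome, so a bias in it has nothing to offset it.

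**Working it through.** **1. The plan's own figure.** SAP D.8 states at least 95% power for a 2-fold increase from 25%, with 150 app patients, 450 controls and alpha 0.05. Sidedness is not stated; two-sided is assumed. For two proportions, power = Φ[(p1 − p2 − 1.96·SE0)/SE1], where SE0 uses the pooled rate and SE1 the separate rates.
- 50% against 25%: pooled rate 31.25%, SE0 = 0.0437, SE1 = 0.0456. Power = Φ[(0.25 − 0.0857)/0.0456] = Φ(3.60) = 99.98%.
- Read as a hazard ratio of 2, power is 98.0–98.4%. Read as an odds ratio of 2 (40% against 25%), it is 93.0%.

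The risk-ratio and hazard-ratio readings meet the stated figure, and the odds-ratio reading comes within 2 points. The issue is bias, not power.

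**2. What each group is screened on.**

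| | App patients | Controls |
|---|---|---|
| Provider or records criterion | Yes (Protocol III) | No (SAP D.2.a) |
| Partners PCP *no* level | Non-Partners or missing | Non-Partners or missing |
| Rehabilitation counted | Partners facilities only | Partners facilities only |

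The last two rows are the same for both groups. The asymmetry is in the first row, and the second row prevents matching from removing it.

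**3. Illustrative size.** The documents do not say how many controls lack a recorded PCP or how often they enrol. Assume:
- 25% enrolment otherwise (the D.8 baseline);
- m = the share of controls of this kind in excess of the app group;
- r = their recorded enrolment rate, taken as 0% to 10%.

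Observed control rate = (1 − m) × 25% + m × r. Inflation of the ratio = 25% / observed control rate.

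| m | r | Control rate | Inflation | Chance of a significant result favouring the app, no true effect |
|---|---|---|---|---|
| 0 | – | 25.0% | 1.00 | 2.5% |
| 10% | 10% | 0.9 × 25 + 0.1 × 10 = 23.5% | 1.064 | 5.8% |
| 10% | 0% | 0.9 × 25 = 22.5% | 1.111 | 9.6% |
| 20% | 10% | 0.8 × 25 + 0.2 × 10 = 22.0% | 1.136 | 12.0% |
| 20% | 0% | 0.8 × 25 = 20.0% | 1.250 | 26.2% |

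The last column uses the formula in step 1 with p1 = 25% and p2 = the observed control rate. For the bottom row, SE0 = 0.0386 and SE1 = 0.0401, so Φ[(0.05 − 0.0756)/0.0401] = Φ(−0.64) = 26.2%. It treats the comparison as two independent proportions and ignores both the matching and the Cox model, so it is a guide to scale only.

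**The case against.** A reader might infer that app patients are traceable, that their matched controls are untraceable, and that the controls' missing outcomes are then set to *no*. The documents do not support that, for four reasons.

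- **The criterion does not secure capture at Partners.** Any long-term Massachusetts provider, or Care Everywhere records, satisfies it. An app patient who attends rehabilitation outside Partners is scored *no* under D.7, just as a control is.
- **A blank PCP field is not proof of having no provider.** The protocol asks for a long-term provider, not a PCP, so an app patient could qualify through a cardiologist and still have a blank field. A control with a blank field may be under a Partners cardiologist, while a recorded outside PCP may point to rehabilitation elsewhere. The direction within the *no* level is therefore not certain.
- **The missing-data rule is not the mechanism.** E.3 begins "Missing data values for participants who fit inclusion criteria will default to zero or" *no* for dichotomous variables, and does not clearly cover controls. Having no Partners rehabilitation record is a *no* by the D.7 definition; it is not a missing value.
- **The gap does not come from D.6.a alone.** Controls go unscreened because D.2.a states no such criterion. Restoring the line in D.6.a would not by itself change which controls are drawn.

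Matching on state, insurance and site also reduces the problem. It does not remove it: State in D.7 is the patient's residence, so two Massachusetts residents, one with a PCP and one without, still match. Finally, even the largest inflation illustrated, 1.25, would leave an observed 2-fold ratio at 2/1.25 = 1.6.

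All of this limits how strongly the point can be put. The difference in eligibility, and the blindness of the two-level factor to it, still stand. A separate asymmetry is that only "subjects who are enrolled in the study will be contacted by a member of the study staff to determine clinical outcomes" at 90 days. That would matter if information on care elsewhere were counted for app patients, which the Partners-only definition does not provide for.

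**Conclusion.** The point holds as a documented difference in eligibility that neither matching nor adjustment can correct as planned. The bias probably favours the app, on the assumption that controls with no recorded PCP use Partners rehabilitation and clinics less than screened app patients do. That assumption is plausible, but the documents do not prove it. Its size is unknown: the 6–25% inflation rests on assumed excess shares of 10–20% and enrolment of 0–10% in those controls. If blank PCP fields are equally common in both groups, and those patients enrol at the same rate, the effect largely cancels. At this scale it could not produce a 2-fold ratio, but it could turn a null result into a nominally significant one more often than the stated alpha allows.

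**What to change.** 1. Reconcile the inclusion lists in Protocol section III and SAP D.6.a. State in D.2.a a record-based form of the provider/records criterion, and apply it identically to app patients and controls before matching. It should not be a rule that only controls must have a recorded PCP: the protocol does not ask that of app patients, so it would create the opposite imbalance. Nor can it rest on the PCP's location, which is not a variable in D.7.
2. Recode the factor in D.7 as Partners PCP, other recorded PCP, or none recorded, in both groups. Match and adjust on the three levels, without first removing patients who have none recorded.
3. Report the number with a missing PCP in each group.
4. Name the Partners PCP = *yes* stratum, already listed among the covariates and subgroups in E.2, as a sensitivity analysis of the primary outcome.

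The cost is SAP wording, an added eligibility step in both groups, and a recode of a variable already planned. The pool of eligible matches will be somewhat smaller, and the analysis restricted to Partners PCP = *yes* will be less precise.

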Should the study staff or health advocate receive clinical questions from subjects, these questions will be directed to the study doctors. For questions that are not appropriate for the study doctors to answer, the study doctors will facilitate contact with one of the subject's healthcare providers.

Study staff will use the electronic medical records to determine the following, and post this information to the subject's Wellframe application:

- What type of stent they have (also used to determine care program outlined below)
- Location of stent: which artery
- Catheter insertion site: wrist or leg
- Discharge Instructions

Study staff will be alerted by Wellframe on the Clinician Dashboard when:

- Subject has not entered medications 3 days after onboarding with Wellframe:
 - Study Staff will send a message encouraging the patient to enter their medications using the clinician messaging system.
- Subject has entered their medications:
 - Study staff will then reconcile the patient reported medication list with the discharge medication list on the subject's medical record.

If any medications entered into the Wellframe account are incorrect, study staff will encourage the subject to consult their discharge medication list and their healthcare provider to ensure they are taking their medications correctly.

PCI Care Programs

Patients will go through two programs. The content provided to patients will be reviewed by the study cardiologists.

During Program 1 subjects will be enrolled in 1 of 3 modules based on what kind of procedure/stent the subject had (Bare Metal Stent, Drug-Eluting Stent, or Angioplasty); all patients will get the coronary artery disease (CAD) module during Program 1. Program 1 will last for approximately 30 days.

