% of patients who attend at least one clinic-based cardiology follow up appointment within 4 weeks of discharge.

Outcome	Exposure(s)	Tables
OP CV F/U	Wellframe	
OP CV F/U	Wellframe + age + sex + insurance + state + DM2 + Partners PCP	

4. Comparison of Exploratory Outcomes:

30D Outcomes: All Cause Hospital, CV Hospital, All Cause ER, CV ER, CV FU and CR

A. 30 day readmission (All cause) (Cox Proportional Hazards Model)

Outcome	Exposure(s)	Tables
All Cause 30d	Wellframe	
All Cause 30d	Wellframe + age + sex + insurance + state + DM2 + Partners PCP	

B. 30 day readmission (CV related) (Cox Proportional Hazards Model)

Outcome	Exposure(s)	Tables
CV 30d	Wellframe	
CV 30d	Wellframe + age + sex + insurance + state + DM2 + Partners PCP	

C. MACE (Cox Proportional Hazards Model)

Outcome	Exposure(s)	Tables
MACE	Wellframe	
MACE	Wellframe + age + sex + insurance + state + DM2 + Partners PCP	

D. 90 day readmission (All cause) (Cox Proportional Hazards Model)

Outcome	Exposure(s)	Tables
All Cause 90d	Wellframe	
All Cause 90d	Wellframe + age + sex + insurance + state + DM2 + Partners PCP	

E. 90 day readmission (CV related) (Cox Proportional Hazards Model)

Outcome	Exposure(s)	Tables
CV 90d	Wellframe	
CV 90d	Wellframe + age + sex + insurance + state + DM2 + Partners PCP	

4. Engagement (Data from Wellframe)

Table 4.1

	90-day
Conversion Rate	
Enrolled/Total PCI	%
Enrolled/Approached	%
Average Days Enrolled	##
Average Medication Reminders	##
Average Patient Satisfaction	##
Average Clinical Messages	%
Average Days to First Message	##
Average Patient Messages Received	##
Average Patient Messages Opened	%
Average Patient Message Response	%
Average Patient Messages Sent	##
Average Patient Physical Activity	%

i. Conversion Rate (# pt enrolled in Wellframe out of # eligible)

- a. Percentage of patients enrolled / total PCI
- b. Percentage of patients enrolled / approached

Table 4.2

	30-day	90-day
Medication Adherence	%	%
Content Completion	%	%
Survey Completion	%	%
Weekly Patient Engagement	%	%
Daily Patient Engagement	%	%

Table 4.3: Predictors of Engagement: Pearson Correlation Analysis

Outcome	Exposure(s)	Figure
Daily Engagement 30d	Age + Sex + DM2 + knownCAD + HTN + HLD + MI/Elective + PAD	Correlation Matrix
Daily Engagement 90d	"	
Weekly Engagement 30d	"	
Weekly Engagement 90d	"	

Table 4.4: Sentiment Analysis (what the messages are about)

Table 4.5: Matrix of correlation between the different engagement values given by Wellframe

FIGURES:

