1. Cardiac Rehabilitation Enrollment: Bar Plot (Intervention Group vs Control Group)
2. App Engagement: Bar Plot (Percentage of Days With App Engagement)
3. Outpatient Cardiac Follow Up: Bar Plot (Intervention Group vs Control Group)
4. 30-Day and 90-Day Readmission Rates: 2 Panel Bar Plot (Intervention Group vs Control Group)
5. App/Dashboard Representative Image (From Wellframe)
6. Process Outcomes: Flow chart of recruitment/enrollment.
7. Daily Engagement and Clinical Outcomes [CR Enrollment, CVFU, 30 Day Readmission, 90 Day Readmission]: 4 Panel Bar Plot (Intervention Group vs Control Group)
8. Predictors of Engagement: Correlation Matrix (Daily/Weekly Engagement Rates vs Traditional CV Risk Factors [Age, Sex, Known CAD, MI, PAD, DM2, HTN, HDL])

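### SAP D.7 counts coronary disease diagnosed at the index PCI, so the exploratory known-CAD predictor of engagement is constant or nearly so

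*SAP*

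**What the plan says.** SAP D.7 defines the study variable Coronary Artery Disease as "Chart diagnosis of CAD prior to or at time of incident PCI or history of CABG or prior PCI". The three routes to a yes are joined by *or*, so any one is enough. D.7 defines no other variable for coronary history.

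The SAP inclusion criteria (D.6.a) require that the patient "underwent PCI at either MGH or BWH during screening period for either symptomatic CAD or ACS". The protocol describes the same population: its sample size statement (Section III) gives "100 with myocardial infarction, 50 with symptomatic coronary artery disease without myocardial infarction", all post-PCI. Its PCI Care Programs section treats coronary disease as universal: "all patients will get the coronary artery disease (CAD) module during Program 1".

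The variable is used in two places. SAP Table 4.3, titled "Predictors of Engagement: Pearson Correlation Analysis", lists the exposures "Age + Sex + DM2 + knownCAD + HTN + HLD + MI/Elective + PAD" against daily and weekly engagement at 30 and 90 days. Item 8 of the SAP's closing list of figures plots engagement against "Age, Sex, Known CAD, MI, PAD, DM2, HTN, HDL".

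SAP E.3 sets missing dichotomous values to no. SAP K treats everything other than 90-day cardiac rehabilitation enrolment as exploratory.

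**The concern.** The label *known CAD* suggests disease established before the index event, as opposed to a first presentation. The coding rule does not make that distinction, because a diagnosis made at the index PCI counts. The same before-or-at-PCI window does little harm for hypertension, hyperlipidaemia, diabetes or peripheral arterial disease, since none of those is the reason for the procedure. Coronary disease is the reason for the procedure. The informative component, earlier CABG or PCI, is lost because the first clause has already produced a yes.

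At stake is one predictor in the engagement analysis. An undefined coefficient leaves an empty cell, which is untidy but visible. The worse case is a handful of no codes. A coefficient is then printed and could be read as first presentations versus established disease, when it actually separates patients by how completely their charts were coded.

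**Working it through.** The documents state no prevalence, sample size or power for this variable, so there is no figure to reproduce. The check has a logical step and a numerical one.

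**Step 1: apply the D.7 rule to the D.6.a population.**

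- Symptomatic CAD without MI (50 of 150 in the protocol): these patients enter because of coronary disease, so they are yes by the entry criterion.
- MI treated by PCI (100 of 150): a CAD diagnosis charted at the time of the procedure is expected but not guaranteed. A chart might carry the MI code without a CAD code.
- Missing entries become no under E.3.

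The expected result is all yes, or nearly all, with the exceptions coming mainly from charting.

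**Step 2: the correlation when everyone is coded yes.** Pearson's r divides by the product of the two standard deviations. With 150 of 150 coded 1, the standard deviation of the predictor is 0 and r is undefined. Running it on a constant vector of 150 returned NaN. This applies to all four outcomes in Table 4.3 (daily and weekly, 30 and 90 days).

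**Step 3: the correlation when a few are coded no.** Testing Pearson's r with a 0/1 predictor is equivalent to comparing two means. With n0 coded no and n1 coded yes, in within-group SD units:

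- SE = √(1/n0 + 1/n1)
- minimum detectable difference = (1.960 + 0.842) × SE
- power for a difference of 0.5 SD = Φ(0.5/SE − 1.960)

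Inputs: n0 + n1 = 150 is the planned enrolment in the SAP. Two-sided alpha 0.05, 80% power and the 0.5 SD difference are assumptions made for this check. The splits are also assumed, because the documents give none.

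| Coded no / yes | Share yes | SE | Minimum detectable difference | Power for 0.5 SD |
|---|---|---|---|---|
| 0 / 150 | 100% | undefined | undefined | undefined |
| 2 / 148 | 98.7% | 0.712 | 1.99 SD | 10.4% |
| 3 / 147 | 98.0% | 0.583 | 1.63 SD | 13.5% |
| 8 / 142 | 94.7% | 0.363 | 1.02 SD | 28.0% |
| 15 / 135 | 90.0% | 0.272 | 0.76 SD | 45.1% |
| 45 / 105 | 70.0% | 0.178 | 0.50 SD | 80.1% |
| 75 / 75 | 50.0% | 0.163 | 0.46 SD | 86.5% |

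Worked row, 3 versus 147: SE = √(0.3333 + 0.0068) = 0.583; 2.802 × 0.583 = 1.63; 0.5/0.583 − 1.960 = −1.10, and Φ(−1.10) = 0.135.

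The last two rows show what a variable that really divides the sample could do. They are symmetric, so 30% coded yes gives the same result as 70%.

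**Step 4: where the variable is used.** It is absent from the matching list (D.2.b), the covariates in E.2 and H, the Table 1 shell and every Cox shell. The third Cox model's cardiovascular risk factors are HTN, HLD, PAD and DM2. It is not among the covariates named for the engagement regression in Section J. Only Table 4.3 and Figure 8 are touched.

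**The case against.** The strongest reply is that a constant predictor is an inference. The documents report no coding frequencies, and the D.7 phrase could mean CAD already on the chart when the patient presented. The history clause and the label *known CAD* both point to an intention to capture pre-existing disease. On that reading the wording needs clarifying and no analysis has failed.

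Part of this stands. *Nearly every participant* is as far as the text goes; a few no codes are possible. The alternative reading is strained, however, because the rule expressly adds the time of the PCI to the time before it. It would not rescue the variable either. The symptomatic-CAD stratum (50/150 = 33% as planned) would still be essentially all yes, so the variable would overlap with MI/Elective, which Table 4.3 already lists separately.

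It is also fair to say that the reach is small. The coefficients are pairwise, so the other seven predictors in Table 4.3 are unaffected, and a fully constant column would be noticed as soon as the analysis was run. That stands, and it limits the weight of the point. A near-constant column is less obvious, because it yields an ordinary-looking coefficient.

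A reader might go further and infer that this definition confounds the app-versus-control comparison of rehabilitation enrolment. The documents do not support that. The variable enters neither the matching nor any comparative model, so its definition can neither create nor remove such bias. Whether earlier revascularisation should be an adjustment covariate is a separate question. The documents give no imbalance in it and no link between it and rehabilitation enrolment.

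**Conclusion.** The point holds as a limited defect in a stated coding rule. Followed as written, D.7 makes Coronary Artery Disease yes for nearly every participant. The four known-CAD correlations in Table 4.3, and the matching entries in Figure 8, are undefined if all are positive. If a few are not, they have little information and reflect charting gaps, including missing values set to no. Over an assumed 90.0% to 98.7% coded yes, power for a 0.5 SD difference is 45.1% down to 10.4%.

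This rests on two things: that a PCI for symptomatic CAD or ACS normally leaves a CAD diagnosis in the chart by the time of the procedure, and that the engagement population is close to the planned 150. The primary analysis of 90-day cardiac rehabilitation enrolment is unaffected.

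**What to change.** In D.7, define known CAD by one rule for all patients: prior MI, PCI or CABG documented with a date before the index admission. Leave a bare CAD diagnosis out of the rule, since elective patients will nearly all have one before the procedure. A single rule also keeps the variable's meaning the same in MI and elective patients. Use it in Table 4.3 and Figure 8, and report it as a descriptive row in Table 1. If this is not wanted, drop known CAD from Table 4.3 and Figure 8.

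The cost is SAP wording and some recoding of chart history. D.7 already requires earlier CABG and PCI to be looked up, though only as parts of the composite; prior MI is an added item, and the Table 1 row needs the same coding in the matched controls. History held outside Partners records will be under-captured, and E.3 would turn those gaps into no, so the table should carry a footnote saying so. Adding the variable to the third Cox model is optional and is not required by this defect.
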